2.2.1 Clinical

Three clinical studies of bimekizumab have been completed: UP0008 in 39 subjects with mild to moderate plaque psoriasis, RA0124 in 30 healthy volunteers, and PA0007 in 53 subjects with psoriatic arthritis. Two studies (RA0123 and UP0031) are ongoing in subjects with moderate to severe rheumatoid arthritis and in healthy subjects, respectively.

UP0008 was a Phase 1, single ascending dose study in adults with mild to moderate psoriasis affecting $\leq 5\%$ BSA. In this blinded study, single doses of up to 640mg (approximately 8mg/kg in an 80kg adult) were evaluated without any safety concerns. A total of 26 subjects with psoriasis with less than 5% of body surface involvement were treated with a range of single iv doses from 8 to 640mg. There were no clinically relevant safety findings identified at any dose and all doses were well tolerated. The pre-specified exploratory assessment of disease activity showed clinically relevant and statistically significant improvements at the higher doses studied.

RA0124 was a Phase 1, open-label, parallel-group, single-dose study in healthy subjects. The primary objective of this study was to determine the absolute bioavailability of single sc doses of bimekizumab (80mg and 160mg). The secondary objectives were to evaluate the dose proportionality of bimekizumab 80mg and 160mg sc, and to evaluate the safety and tolerability of these sc doses and 160mg given by iv infusion. In RA0124, the absolute bioavailability was similar for the 2 doses tested (0.656 and 0.631 for the bimekizumab 80mg and 160mg sc doses, respectively). The PK of bimekizumab was linear in the tested dose range and the median $t_{1/2}$ following sc administration was similar to that following iv administration (27.81 days and 28.25 days for bimekizumab 160mg sc and 160mg iv, respectively).

Bimekizumab has also been investigated in a Phase 1b, proof of concept, randomized, placebo-controlled, multiple dose study (PA0007). The primary objective of PA0007 was to assess the safety and PK of multiple dose administration of iv bimekizumab in subjects with psoriatic arthritis. Four active doses and a placebo were tested. Drug was administered as a loading dose at Week 0, and 2 additional doses were administered at Week 3 and Week 6. In each treatment group, subjects received a total of 3 doses of bimekizumab, administered every 3 weeks as shown below:

- 80mg loading dose followed by 40mg at Weeks 3 and 6

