9.6 Adverse events for special monitoring

UCB has identified AEs for special monitoring (AESM). An AESM is an AE or safety topic for which special monitoring, additional data collection activities, and/or enhanced signal detection activities (within UCB), are considered appropriate. Identified AESM can be of particular interest based on findings from the IMP clinical program to date, potential risks generally associated with biologic immunomodulators, or comorbidities and risk factors prevalent in the study population.

Adverse events for special monitoring for this study include: serious infections (including opportunistic infections and TB; see [Section 9.8.1](#)), cytopenias, hypersensitivities, suicide ideation or behavior (assessed using the eC-SSRS; see [Section 9.8.6](#)), depression and anxiety (assessed using the HADS; see [Section 12.9](#)), major cardiovascular events, and liver function test changes/enzyme elevations (ALT, AST, bilirubin; see [Section 9.7.1](#)), malignancies, and inflammatory bowel diseases.

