≥3xULN (and ≥2x baseline) and <5xULN (and ≥2x baseline)	<2xULN	No	Discussion with Medical Monitor required. Consider need for hepatology consult if there is no evidence of resolution (see Follow up requirements). ^c	Further investigation – immediate IMP discontinuation not required (see Section 9.7.1.2). IMP discontinuation required if any of the following occur: 
 • Subject cannot comply with monitoring schedule. • Liver chemistry values continue to increase. • Liver chemistry values remain ≥3xULN (and ≥2x baseline) after 2 weeks of monitoring without evidence of resolution. 	Essential: Every attempt must be made to have repeat liver chemistry values and additional testing completed within 48 hours at the site with HCP (see Section 9.7.1.3).	Monitoring of liver chemistry values at least twice per week for 2 weeks. ^d 
 • Immediate IMP discontinuation required if liver chemistry values continue to increase. After 2 weeks of monitoring liver chemistry values: 
 • Discontinue IMP if levels remain ≥3xULN (and ≥2x baseline) without evidence of resolution^d • Continue to monitor until values normalize, stabilize, or return to within baseline values.^d

ALT=alanine aminotransferase; ASAP=as soon as possible; AST=aspartate aminotransferase; HCP=healthcare practitioner; IMP=investigational medicinal product; NA=not applicable; PDILI=potential drug-induced liver injury; ULN=upper limit of normal

^a Hepatitis symptoms include fatigue, nausea, vomiting, and right upper quadrant pain or tenderness; hypersensitivity symptoms include eosinophilia (>5%), rash, and fever (without clear alternative cause).

^b If the subject also has ≥2xULN alkaline phosphatase, the possibility of an indication of biliary obstruction should be discussed with the Medical Monitor.

^c Details provided in [Section 9.7.1.1](#). The local hepatologist is the expert usually consulted by the treating physician for assessment and management of potential hepatic disease. This would usually be a hepatologist, but may be a gastroenterologist.

^d Unless an alternative monitoring schedule is agreed by the Investigator and UCB responsible physician. Determination of stabilization is at the discretion of the Investigator in consultation with the hepatologist (as applicable) and UCB responsible physician, as needed.

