 - All serious TEAEs which code to a PT included in any of the following HLTs: Heart Failures NEC, Left Ventricular Failures, or Right Ventricular Failures and which also code to the SOC of Cardiac Disorders as Primary SOC.

4. Cytopenias

These events will be presented in a stand-alone table that is based on the SMQ = “Haematopoietic cytopenias”. The SMQ search should include all serious TEAEs which code to a PT included in the Scope = Broad and/or Scope = Narrow groups within the SMQ.

5. Neuropsychiatric events (in particular depression and suicide)

These events will be presented in a stand-alone table including EAIR and EAER. The table will be based on the SMQ = “Depression and suicide/self-injury (SMQ)”. The SMQ search will include all TEAEs which code to a PT included in the Scope = Broad and/or Scope = Narrow groups within the SMQ.

6. Inflammatory bowel disease

These events will be presented in a stand-alone table which includes EAIR and EAER. The table will include all TEAEs which code into the HLT of “Colitis (excl infective)”.

7. Anaphylactic reaction

Anaphylactic reactions will be summarized together in a stand-alone table.

The first row within the body of the table will be labeled “Any hypersensitivity reaction/anaphylactic reaction” and will represent the overall incidence of subjects who reported at least one hypersensitivity reaction or at least one anaphylactic reaction.

The second row within the body of the table will be labeled “Any hypersensitivity reaction” and will represent the overall incidence of subjects who reported at least one hypersensitivity reaction.

The third row within the body of the table will be labeled “Any anaphylactic reaction” and will represent the overall incidence of subjects who reported at least one anaphylactic reaction.

Following these three overall incidence rows, all TEAEs that have been identified as either a hypersensitivity reaction or an anaphylactic reaction will be summarized (together – not broken out by type) by SOC, HLT and PT.

Hypersensitivity reactions and anaphylactic reactions will be identified as follows:

a) Hypersensitivity reactions

All TEAEs that either emerged on the same day as when a study medication injection reaction was received, or that emerged one day after a study medication injection was received, which code to a PT which contains the term “hypersensitivity” will be considered to be a hypersensitivity reaction and included in the summary table as such.

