b) Anaphylactic reactions

An algorithmic approach will be used to identify TEAEs that are considered to be anaphylactic reactions. PTs are separated into the four distinct categories (A, B, C, D) prior to the algorithmic approach being applied.

All TEAEs that either emerged on the same day as when a study medication injection reaction was received, or that emerged one day after a study medication injection was received, and which fulfill any of the three criteria described in [Section 12.3](#) will be included in the summary table.

8. Hepatic events and DILI

Although not officially considered to be AEs of special monitoring, hepatic events are nonetheless considered to be interesting enough to be summarized in stand-alone tables.

Hepatic events will be summarized in a stand-alone table that includes all TEAEs in the SMQ “Drug related hepatic disorders – comprehensive search (SMQ)”. Note that the following two sub-SMQs are to be excluded: “Liver neoplasms, benign (incl cysts and polyps)” and “Liver neoplasms, malignant and unspecified (SMQ)”.

The SMQ search should include all TEAEs (regardless of whether they have been judged as related to study medication or not) which code to a PT included in the Scope = Narrow group within each SMQ.

Hy’s Law cases are to be reported separately in the liver function test summary table (with adjudication for “Potential drug-induced liver injury” cases).

Additional tables will summarize TEAEs by responder status (defined as PS0010 Week 12 PASI90 response):

- Incidence of TEAEs – Overview
- Incidence of TEAEs per 100 subject years by SOC, HLT and PT
- Incidence of Serious TEAEs per 100 subject years by SOC, HLT and PT
- Incidence of Fungal Infectious Disorders per 100 subject years by SOC, HLT and PT

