12.3 MedDRA algorithmic approach to anaphylaxis

The SMQ *Anaphylactic reaction* consists of three parts:

- A **narrow search**: If a subject reports any TEAE which codes to a PT included in Category A, then the event will be flagged as an anaphylactic reaction and summarized as such in the table
- Category A

- SMQ Anaphylactic reaction (SMQ)
 - PT Anaphylactic reaction
 - PT Anaphylactic shock
 - PT Anaphylactic transfusion reaction
 - PT Anaphylactoid reaction
 - PT Anaphylactoid shock
 - PT Circulatory collapse
 - PT Dialysis membrane reaction
 - PT Kounis syndrome
 - PT Shock
 - PT Shock symptom
 - PT Type I hypersensitivity

- A **broad search**: If a subject reports any TEAE which codes to a PT included in Category B **AND** reports any TEAE which codes to a PT included in Category C, **and both TEAEs have the same start date**, then both events will be flagged as anaphylactic reactions and summarized as such in the table
- Category B

- PT Acute respiratory failure
- PT Asthma
- PT Bronchial oedema
- PT Bronchospasm
- PT Cardio-respiratory distress
- PT Chest discomfort
- PT Choking
- PT Choking sensation
- PT Circumoral oedema
- PT Cough
- PT Cyanosis
- PT Dyspnoea
- PT Hyperventilation
- PT Irregular breathing
- PT Laryngeal dyspnoea
- PT Laryngeal oedema
- PT Laryngospasm
- PT Laryngotracheal oedema
- PT Mouth swelling
- PT Nasal obstruction
- PT Oedema mouth
- PT Oropharyngeal spasm
- PT Oropharyngeal swelling
- PT Respiratory arrest
- PT Respiratory distress
- PT Respiratory dyskinesia
- PT Respiratory failure
- PT Reversible airways obstruction
- PT Sensation of foreign body
- PT Sneezing
- PT Stridor
- PT Swollen tongue
- PT Tachypnoea
- PT Throat tightness
- PT Tongue oedema
- PT Tracheal obstruction
- PT Tracheal oedema
- PT Upper airway obstruction
- PT Wheezing

- Category C

+	PT	Allergic oedema	
+	PT	Angioedema	
+	PT	Erythema	
+	PT	Eye oedema	
+	PT	Eye pruritus	
+	PT	Eye swelling	
+	PT	Eyelid oedema	
+	PT	Face oedema	
+	PT	Flushing	
+	PT	Generalised erythema	
+	PT	Injection site urticaria	
+	PT	Lip oedema	
+	PT	Lip swelling	
+	PT	Nodular rash	
+	PT	Ocular hyperaemia	
+	PT	Oedema	
+	PT	Periorbital oedema	
+	PT	Pruritus	
+	PT	Pruritus allergic	
+	PT	Pruritus generalised	
+	PT	Rash	
+	PT	Rash erythematous	
+	PT	Rash generalised	
+	PT	Rash pruritic	
+	PT	Skin swelling	
+	PT	Swelling	
+	PT	Swelling face	
+	PT	Urticaria	
+	PT	Urticaria papular	

- Category D

+	PT	Blood pressure decreased
+	PT	Blood pressure diastolic decreased

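### The SAP's hypersensitivity row excludes isolated urticaria or angioedema and every reaction starting more than one day after an injection, and the same flag steers attribution on the switch date

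*SAP*

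**What the plan says.** Protocol 9.6 lists the adverse events for special monitoring (AESM). The list includes "cytopenias, hypersensitivities, suicide ideation or behavior", with no restriction on preferred term (PT) or on time since dosing.

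SAP 8.2.1 handles this topic in item 7, headed as anaphylactic reaction. One table carries three overall rows: either type, any hypersensitivity reaction, and any anaphylactic reaction. Below these, "all TEAEs that have been identified as either a hypersensitivity reaction or an anaphylactic reaction will be summarized" by SOC, HLT and PT. There are two ways in.

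- **Item 7a, hypersensitivity.** The same-day limb begins "All TEAEs that either emerged on the same day as when a study medication injection reaction was received". The next-day limb covers events "that emerged one day after a study medication injection was received, which code to a PT which contains the term" hypersensitivity. The word requirement applies to both limbs.
- **Item 7b, anaphylaxis.** The onset window is the same, for events in it "and which fulfill any of the three criteria described in" SAP 12.3. The criteria are a Category A term; a Category B term with a Category C term; or a Category D term with a B or C term. Pairs must share a start date, and "then both events will be flagged as anaphylactic reactions and summarized as such in the table". Urticaria, angioedema, rash and pruritus are all Category C terms.

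SAP 8.2.1 uses the same identification in the tables that combine PS0010 and PS0011. An event on the PS0011 Baseline date goes to the PS0010 treatment unless it falls under the injection-site-reaction HLT, is marked on the AE CRF as an injection reaction (and does not code to the Investigations SOC), or has been identified as a hypersensitivity or anaphylactic reaction.

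**The concern.** A topic that the protocol names without limits becomes, in the SAP, a text match on one word plus a two-day window. No reason is given, and no other AESM item covers the topic. Items 1 to 6 search by SOC, HLGT, HLT, SMQ or a defined term list, and none of them sets an onset window.

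Two things are at stake. First, the row label begins with *Any*, so a reader will take it as the total. In a study whose primary objective is long-term safety and tolerability, it could show few or no cases while allergic reactions sit in separate rows of the general tables. Second, the flag affects attribution. A subject who moves from placebo to bimekizumab could have an allergic event after the first active injection and see it counted under placebo in the combined tables.

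**Working it through.** **Which events enter the table.** Applying items 7a and 7b with SAP 12.3:

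| Event | Hypersensitivity row | Anaphylaxis row | Combined row |
|---|---|---|---|
| PT containing the word, day after injection | yes | no, unless 12.3 is also met | yes |
| PT containing the word, three days after injection | no | no | no |
| Urticaria or angioedema alone, injection day | no | no | no |
| Urticaria plus dyspnoea (C with B), same start date, in window | no | yes | yes |
| Angioedema plus hypotension (C with D), same start date, in window | no | yes | yes |
| Either pair, three days after injection | no | no | no |

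Two kinds of event are therefore absent from all three rows: isolated Category C events, and every event with onset later than the day after an injection.

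**How much of the TEAE period the window covers.** The plan states no figure for this. Inputs:

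- A completer has 24 expected injections, two per dose (SAP 7): 24 / 2 = 12 doses.
- The TEAE period runs from the first dose to the last dose + 140 days (SAP 8.1.1).
- Exact 28-day spacing is assumed.

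Eligible onset days: 12 × 2 = 24.

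TEAE period: (12 − 1) × 28 + 140 = 308 + 140 = 448 days.

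Share: 24 / 448 = 5.4%. The other 424 days (94.6%) cannot contribute an event. Between doses the share is 2 / 28 = 7.1%.

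Protocol Table 5-1 also marks an administration at Week 48, which Protocol 8.8 and the SAP's injection count do not include. With 13 doses the share is 26 / (12 × 28 + 140) = 26 / 476 = 5.5%, so the result does not depend on that discrepancy.

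**Switch date.** Take a placebo subject in PS0010 without a PASI90 response, who receives bimekizumab 160mg at PS0011 Baseline and has angioedema alone that day.

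1. The PT does not contain the required word, so item 7a fails.
2. There is no same-date B or D term, so item 7b fails.
3. Suppose the site does not mark it as an injection reaction on the CRF and it is not coded under the injection-site HLT. Then no exception applies.
4. The combined tables of TEAEs and of serious TEAEs per 100 subject-years count it under placebo.

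The tables for PS0011 alone are unaffected, because events starting on the first-dose date are treatment-emergent there.

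**Wording of the same-day limb.** Items 7a and 7b both refer to the day an injection reaction was received; the next-day limb refers to an injection. Taken literally, a same-day event would need a recorded injection reaction to qualify.

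**The case against.** The strongest reply is that no data are lost. The primary safety analysis covers all TEAEs by SOC, HLT and PT, with EAIR, confidence interval and EAER, and the excluded events are counted there and in the listing of all TEAEs. The study is descriptive, so the effect is limited to one secondary display and one attribution rule. This stands, and it limits the weight of the point. It does not repair the row: a subject may have several allergic terms, so the number of subjects with any hypersensitivity event cannot be obtained by adding PT rows.

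It can also be said that item 7 is an acute post-injection table, for which a short window is coherent; that Protocol 9.6 names topics and not analysis definitions; and that the SAP narrows other AESM too, taking only serious events for cytopenias and major cardiovascular events. An acute table is a legitimate choice. It then needs that label, and the wider topic is left without a summary.

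A reader might infer more than the documents support:

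- **That urticaria and angioedema are missing altogether.** Paired with a same-date B or D event inside the window, they enter the anaphylaxis and combined rows.
- **That about 95% of reactions are missed, or that the reported rate will be far below the true one.** The 94.6% is calendar time. No onset distribution or term frequencies are given; if reactions cluster around injections, the window may lose few.
- **That the protocol defines this topic by its liver-injury footnote, "hypersensitivity symptoms include eosinophilia (>5%), rash, and fever (without clear alternative cause".** That footnote in Table 9-3 serves the evaluation of raised transaminases, not this AESM.
- **That the half-life in Protocol 2.2.1 ("27.81 days and 28.25 days for bimekizumab 160mg sc and 160mg iv, respectively") implies late reactions.** It shows drug persistence; the documents do not link it to delayed hypersensitivity.

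The injection-reaction wording is very probably a slip. It still needs correcting, because it appears in both rules.

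**Conclusion.** The point holds in a limited form. Followed as written, item 7 leaves out isolated urticaria or angioedema and all reactions starting more than one day after an injection, from the only AESM table on a topic that the protocol names without limits. The row may understate incidence and can show zero; by how much cannot be derived. The 5.4% (24 of 448 days, assuming 12 doses at 28-day spacing) describes the window and not the loss.

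The attribution effect is confined to events on the switch date, in the combined PS0010/PS0011 tables, that meet none of the three exceptions. The number of such events is unknown and may be small. The primary analysis is not affected. The change is still worth making, because the row is labelled as a total and the missing events are already coded.

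**What to change.** In SAP 8.2.1 item 7:

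1. Add a row for all TEAEs found by a standard hypersensitivity search, regardless of timing, with EAIR and EAER by PS0011 treatment group. The narrow scope of the MedDRA Hypersensitivity SMQ is one option. Its contents are not in the documents, so its yield should be checked first. If it proves too broad, the SAP's own Category C list taken unpaired, plus PTs containing the word, would capture the isolated terms.
2. Keep the events now selected, on the injection day or the next, as a row labelled acute. Nothing currently planned is lost.
3. Use the fuller search for the switch-date exception, in both the TEAE and the serious-TEAE paragraphs.
4. In items 7a and 7b, make the same-day limb refer to an injection instead of an injection reaction.

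The cost is SAP wording, one reprogrammed table and one changed attribution flag, all from data already coded. The downside is that the any-time row will take in some unrelated rash or allergy terms in a psoriasis population; the acute row beside it helps the reader judge this.

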8.2 Other safety analysis

8.2.1 TEAEs

The following summaries will be provided by PS0011 treatment group and for the “All bimekizumab” group. In addition, all summaries of TEAEs “per 100 subject years” will display EAIR and EAER:

- Incidence of TEAEs – Overview
- Incidence of TEAEs per 100 subject years by SOC, HLT and PT
- Incidence of TEAEs per 100 subject years by SOC, HLT, PT and by Timing of Onset Relative to Anti-bimekizumab Antibody Status
- Incidence of TEAEs by Decreasing Frequency of PT
- Incidence of TEAEs by Maximum Severity, SOC, HLT and PT
- Incidence of Non-Serious TEAEs by SOC, HLT and PT
- Incidence of Non-Serious TEAEs Above Reporting Threshold of 5% by SOC and PT

The incidence of TEAEs per 100 subject years will also be summarized for PS0010 and PS0011 combined, where treatment emergence and exposure at risk are relative to the first dose of study drug in PS0010. In the case of a subject that switches study treatment when starting PS0011, exposure at risk to PS0010 treatment will end the day prior to the first PS0011 dose. Adverse events that occur on the PS0011 baseline visit date will be attributed to the PS0010 treatment.

The only exception to this definition is for the following types of events:

- Those that code to a High Level Term (HLT) of “Injection Site Reactions”
- Those which have been designated as an Injection Reaction on the AE CRF and do not code to a System Organ Class (SOC) of “Investigations”
- Those which have been identified as a hypersensitivity reaction or an anaphylactic reaction

When any of these events occur on the date of treatment switch at PS0011 Baseline, the AE will be attributed to the treatment initiated in PS0011.

All AE summaries will be ordered alphabetically by SOC and HLT within SOC and in terms of decreasing frequency for PT within HLT in the “All bimekizumab” treatment group.

For each subject and each AE, the worst severity recorded will be attributed and used in the by-severity summaries. Similarly, the worst causality (most related to treatment) will be attributed and used in the by-causality summaries. If severity or causality is missing, the worst case will be assumed.

If the intensity of an AE is unknown, it will be considered as severe. If the relationship to study drug is missing, it will be considered as related.

Additional tables will summarize TEAEs by relationship to study medication, TEAEs leading to withdrawal from the study, treatment-emergent SAEs, and deaths:

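### The same-day limb of the hypersensitivity and anaphylaxis rule in SAP 8.2.1 depends on an injection reaction instead of an injection, so read literally it can drop dosing-day events.

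*SAP*

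**What the plan says.** SAP Section 8.2.1, AESM item 7, defines a stand-alone table of hypersensitivity and anaphylactic reactions. In item 7b the first timing limb is "All TEAEs that either emerged on the same day as when a study medication injection reaction was received". The second limb, and its link to the appendix, reads "or that emerged one day after a study medication injection was received, and which fulfill any of the three criteria described in" Section 12.3. Item 7a uses the same two timing limbs for preferred terms containing the word hypersensitivity.

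Section 12.3 lists the coding criteria for anaphylaxis. For the narrow search it says: "If a subject reports any TEAE which codes to a PT included in Category A, then the event will be flagged as an anaphylactic reaction". It states no timing relative to dosing.

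The flag is used again earlier in Section 8.2.1: "The incidence of TEAEs per 100 subject years will also be summarized for PS0010 and PS0011 combined", and the same is planned for serious TEAEs. In those combined tables the default for the switch day is: "Adverse events that occur on the PS0011 baseline visit date will be attributed to the PS0010 treatment". Three kinds of event are excepted and go to the PS0011 treatment:

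- events in the injection site reactions HLT;
- events "designated as an Injection Reaction on the AE CRF" that do not code to the Investigations SOC;
- "Those which have been identified as a hypersensitivity reaction or an anaphylactic reaction".

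**The concern.** The two limbs of one timing rule have different triggers. A subject receives an injection, not a reaction, so the same-day limb looks like a slip. It can nevertheless be programmed, because the AE CRF carries an Injection Reaction designation that matches the literal words. Section 8.2.1 also lists CRF-designated injection reactions and identified hypersensitivity or anaphylactic reactions as separate exceptions, so the SAP does not treat them as one set.

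Two outputs are at stake. The first is the stand-alone table: protocol Section 9.6 names hypersensitivities for special monitoring, and the literal rule can lose events on the dosing day itself. The second is attribution in the combined tables, where an event that is not identified loses one of its routes to the PS0011 treatment.

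**Working it through.** The plan gives no figure to reproduce. The check counts eligible days and then follows an event through the rules.

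**Inputs**
- SAP Section 7: 24 injections for a subject who completes treatment, two per dose. Dosing days = 24 / 2 = 12 (Baseline to Week 44).
- SAP 8.2.1, items 7a and 7b: the two timing limbs.
- SAP 8.2.1: the switch-day default and its three exceptions.
- SAP 2.3.2: PS0010 placebo subjects without a PASI90 response move to bimekizumab 160mg.
- SAP 2.4: 240 subjects planned for PS0010.

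**Eligible days for a completer**
- Injection in both limbs: 12 dosing days + 12 next days = 24.
- Literal text: 12 next days + any days with a recorded injection reaction. With none recorded, 12, so every dosing day is lost.

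**Following one event that meets the coding criteria.** The last two columns assume that it is not in the injection site reactions HLT.

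| Event day | Injection reaction recorded that day | Literal rule | Injection in both limbs | Switch-day attribution, literal | Switch-day attribution, both limbs |
|---|---|---|---|---|---|
| Dosing day | No | Not identified | Identified | PS0010 | PS0011 |
| Dosing day | Yes | Identified | Identified | PS0011 | PS0011 |
| Next day | No | Identified | Identified | Not applicable | Not applicable |
| Fifth day after dose | No | Not identified | Not identified | Not applicable | Not applicable |

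The readings differ only in the first row.

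**How many subjects could have an event charged to placebo.** Protocol Section 2.2.1 lists six PS0010 regimens but prints a five-term allocation ratio. Assuming six equal arms, the ceiling is 240 / 6 = 40 placebo subjects; with five arms it is 240 / 5 = 48. PASI90 responders and subjects who do not enter PS0011 must be subtracted. For other subjects who switch, the event would be charged to the wrong bimekizumab dose.

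**What does not change.** Under SAP 8.1.1 an event starting on the first PS0011 dosing day is a TEAE, and under 8.1.6 it is summarized by PS0011 treatment group. It therefore stays in the general SOC, HLT and PT tables and in the listing of all TEAEs.

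**The case against.** The strongest reply is that nobody intended this rule. The second limb of the same sentence says injection, and a programmer would probably read the first limb the same way. That is a fair account of the intent and it limits the severity. It does not make the text correct: the wording occurs in both 7a and 7b, and the SAP amendment (Section 13) leaves it alone while its Change #8 adds a switch-day rule that relies on the resulting flag.

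It can also be said that no separate injection reaction is needed. If the investigator designates the anaphylactic event itself as an Injection Reaction, it meets the literal limb and is separately excepted on the switch day (unless it codes to Investigations). That stands. The gap is confined to dosing-day events on days with no designated injection reaction. How often this happens depends on CRF instructions that are not in these documents.

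A reader might infer that Section 12.3, by giving Category A no timing, also causes events to be missed or charged to placebo. The documents do not support this. Item 7b joins its window by *and* to any of the three criteria in Section 12.3, so Category A is time-limited through 8.2.1. Read alone, Section 12.3 could only add events: it would open all of a completer's 44 x 7 + 140 = 448 days at risk (equation 7), including late Category A terms such as shock. That is a reason for a cross-reference and no more.

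**Conclusion.** Wrong as written, minor severity. Followed literally, items 7a and 7b omit from the stand-alone table any hypersensitivity or anaphylactic event on a dosing day with no recorded injection reaction. A completer with no recorded injection reactions keeps 12 of 24 eligible days. This assumes the 12 doses implied by SAP Section 7.

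The attribution error is narrower. It needs the combined PS0010 and PS0011 TEAE or serious-TEAE tables, a subject who changes treatment, an event on the switch day, and no other exception (CRF-designated injection reaction or injection site reaction HLT). A reader might infer that the primary PS0011 safety analysis would count such an event under placebo. It would not, because that analysis uses the PS0011 treatment group. Nor does the SAP specify a combined-study anaphylaxis table in which the event could move between arms. The documents give no expected number of these events, so the effect on reported rates cannot be sized.

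**What to change.** In items 7a and 7b, make both limbs depend on the injection: the event starts on the same day as, or one day after, a study medication injection. A qualifying switch-day event is then identified and goes to the PS0011 treatment, whether or not an injection reaction was recorded.

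For consistency, add a sentence to Section 12.3 saying that the 8.2.1 window applies to all three searches, so that the appendix is not programmed on its own and late Category A events are not over-counted.

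The cost is the same small edit in two items, one cross-reference and a check of the flag in the program. No new data are needed.
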